6.2. Primary Efficacy Variable(s) and Analysis

6.2.1. Variable Definition

The primary efficacy variable for this study is the categorized percent reduction in the daily OCS dose during weeks 20 to 24 as compared with the OCS dose at the end of the optimization phase.

The week 20 to 24 maintenance dose and corresponding values for absolute and percent change (reduction) from baseline will be calculated as follows:

- **Baseline dose** = the prescribed optimized OCS dose following the OCS optimization period ([Table 8](#))
- **Maintenance dose** = mean of all daily OCS doses during the maintenance period extending from Week 20 to Week 24 ([Table 8](#))
- **Absolute reduction** = maintenance dose – baseline dose
- **Percent reduction** = $100 \times (\text{absolute reduction} / \text{baseline dose})$

For both the primary and secondary efficacy analyses, OCS dose will refer to the total daily dose of oral prednisone prescribed for asthma (as per CRF), unless otherwise noted.

The 5 categories for the primary analysis of percent reduction during weeks 20 to 24 are:

- 90% to 100% reduction
- 75% to <90% reduction
- 50% to <75% reduction
- >0% to <50% reduction
- No decrease in OCS, or loss of baseline asthma control during weeks 20 through 24, or discontinuation from study drug

Loss of baseline asthma control will be defined as FEV₁ value of <80% of baseline at the week 24 visit, or clinically significant worsening in ACQ-6 score (increase ≥ 0.5) at the week 24 visit compared with baseline, and/or clinical asthma exacerbation during weeks 20 through 24 (CAE defined in [Section 6.3.3.1](#)).

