6.3.2.1. Variable Definition

6.3.2.1.1. Continuous Variable

The post-baseline values for OCS dose and corresponding values for absolute and percent change from baseline will be calculated as follows:

- **Baseline dose** = the prescribed optimized OCS dose following the OCS optimization period (Table 8)
- **Post-baseline dose** = mean of all daily OCS doses during each defined analysis period (Table 8)
- **Absolute reduction** = post-baseline dose – baseline dose
- **Percent reduction** = $100 \times (\text{absolute reduction} / \text{baseline dose})$

Table 8: Definition of Analysis Days for OCS Dose

Analysis period	Start day	Stop day
Baseline Dose	Day of first dose of study drug	N/A
Baseline to Week 4	Day of first dose of study drug + 1 day	Day of W4 Visit
Week 4 to Week 8	Day of W4 Visit + 1 day	Day of W8 Visit
Week 8 to Week 12	Day of W8 Visit + 1 day	Day of W12 Visit
Week 12 to Week 16	Day of W12 Visit + 1 day	Day of W16 Visit
Week 16 to Week 20	Day of W16 Visit + 1 day	Day of W20 Visit
Week 20 to Week 24 (Maintenance Dose)	Day of W20 Visit + 1 day	Day of W24 Visit

DoR=Day of Randomization

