6.3.2.1.2. Categorical Variable

The proportion of patients achieving a 50% or greater reduction in OCS dose at weeks 20 to 24 will be based on the percent reduction from baseline to weeks 20 to 24. The categories for this analysis are:

- 50-100% reduction
- <50% reduction, or loss of baseline asthma control during weeks 20 through 24, or discontinuation from study drug

The proportion of patients who achieve a reduction of their OCS dose to less than or equal to 5 mg at weeks 20 to 24 will be based on the observed post-baseline value during weeks 20 to 24. The categories for this analysis are:

- ≤ 5 mg
- > 5 mg, or loss of baseline asthma control during weeks 20 through 24, or discontinuation from study drug

The proportion of patients who achieve a total reduction (discontinuation) of their OCS dose at weeks 20 to 24 will be based on the observed post-baseline value during weeks 20 to 24. The categories for this analysis are:

- =0 mg
- > 0 mg, or loss of baseline asthma control during weeks 20 through 24, or discontinuation from study drug

Note: Total reduction implies no OCS use during the entire period (weeks 20 to 24).

The proportion of patients achieving less than a 5 mg reduction in OCS dose at weeks 20 to 24 will be based on the absolute reduction from baseline to weeks 20 to 24. The categories for this analysis are:

- ≥ 5 mg reduction

- <5 mg reduction, or loss of baseline asthma control during weeks 20 through 24, or discontinuation from study drug

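### SAP 6.2.1 and 6.3.2.1.1 compute OCS reduction as later dose minus baseline dose, so every true reduction is negative and misses the positive category bounds of the primary and two secondary endpoints

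*SAP*

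**What the plan says.** SAP 6.2.1 introduces the primary derivation by saying that the "corresponding values for absolute and percent change (reduction) from baseline will be calculated as follows". It sets absolute reduction to "maintenance dose – baseline dose" and percent reduction to 100 × (absolute reduction / baseline dose). The categories below it run from "90% to 100% reduction" down to above 0% but under 50%, and the lowest is "No decrease in OCS, or loss of baseline asthma control during weeks 20 through 24, or discontinuation from study drug".

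SAP 6.3.2.1.1 repeats the two formulas for each analysis period, with absolute reduction equal to "post-baseline dose – baseline dose".

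SAP 6.3.2.1.2 then builds two secondaries on these quantities:

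- The first-ranked secondary "will be based on the percent reduction from baseline to weeks 20 to 24"; its responder category is "50-100% reduction".
- The fourth-ranked secondary "will be based on the absolute reduction from baseline to weeks 20 to 24"; it is cut at a reduction of 5 mg.

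The secondaries for a dose of 5 mg or less and for 0 mg use the observed dose. The third-ranked secondary is a percent change.

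**The concern.** Later dose minus baseline dose is negative whenever the dose falls. The category bounds it feeds are positive, and no section takes an absolute value or reverses the sign. The protocol does not settle it: it lists the categories but gives no formula, and the SAP Introduction says that the SAP prevails where the two differ. The SAP text is therefore the only written derivation of the primary endpoint and of two endpoints in the fixed testing sequence.

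Taken literally, a patient who tapers successfully and keeps asthma control belongs to no primary category and is a non-responder on both secondaries. A patient whose dose rises can be credited with a reduction.

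A less visible effect is in the rank-sum sensitivity analysis of 6.3.2.2.3. Patients who withdraw or lose control are ranked below the smallest observed reduction. On the literal scale the smallest value is the largest true fall in dose, so these patients would rank beyond the best responders, and no unassigned category would flag it.

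**Working it through.** **1. Single patients.** Let b be the baseline dose and m the later dose. As written, absolute = m − b and percent = 100 × (m − b)/b. Corrected, absolute = b − m and percent = 100 × (b − m)/b.

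| b to m (mg) | As written | Category as written | Corrected | Category corrected |
|---|---|---|---|---|
| 20 to 2.5 | −17.5 mg, −87.5% | none; fails the 50% and 5 mg cuts | +17.5 mg, +87.5% | 75% to <90%; meets both cuts |
| 20 to 0 | −20 mg, −100% | none; fails both cuts | +20 mg, +100% | 90% to 100%; meets both cuts |
| 15 to 10 | −5 mg, −33.3% | none; fails both cuts | +5 mg, +33.3% | >0% to <50%; meets the 5 mg cut |
| 10 to 12.5 | +2.5 mg, +25% | >0% to <50%, and also no decrease | −2.5 mg, −25% | no decrease |
| 10 to 15 | +5 mg, +50% | 50% to <75%, and also no decrease; meets both cuts | −5 mg, −50% | no decrease |

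Each corrected value falls where its label says it should. The 20 to 0 mg patient also shows an internal clash: as written, this patient is a responder on the 0 mg secondary and a non-responder on the 50% secondary.

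**2. Every dose in the taper schedule.** SAP Table 3 has nine starting doses with 5 + 5 + 5 + 5 + 5 + 5 + 4 + 3 + 2 = 39 lower doses.

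- As written: 0 of 39 positive, 0 at 50% or more, 0 at 5 mg or more.
- Corrected: 39 of 39 positive, split 11, 9, 12 and 7 over the four categories from best to worst. At 50% or more: 11 + 9 + 12 = 32. At 5 mg or more: 36; the exceptions are 10 to 7.5, 7.5 to 5 and 5 to 2.5 mg.

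**3. Size under the planning assumptions (SAP 2.3).** Inputs: placebo shares 10.9, 7.9, 14.8, 10.8 and 55.6%; odds ratio 2.63; 76 per group.

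The plan's own figure comes first. The Whitehead proportional-odds formula is n per arm = 6(z₀.₉₇₅ + z₀.₉₀)² / [(ln 2.63)² × (1 − Σp̄³)], where p̄ is the mean of the two arms' shares in each category. It gives 74.7, or 75 after rounding up, and power at 76 per arm is 90.5%. The stated 76 per group for 90% power is reproduced. The sign problem does not enter this calculation.

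Cumulative shares from the best category down:

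- Placebo: 10.9, 18.8, 33.6, 44.4%.
- Reslizumab, multiplying each cumulative odds by 2.63: 24.3, 37.8, 57.1, 67.7%. For the last, 0.444/0.556 = 0.799; × 2.63 = 2.100; 2.100/3.100 = 0.677.

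Patients with a true reduction who would have no primary category: 76 × 0.444 = 33.7 and 76 × 0.677 = 51.5, together 85.2 of 152 = 56%.

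Responders missed on the 50% secondary: 76 × 0.336 = 25.5 and 76 × 0.571 = 43.4, together 68.9.

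**4. Intended direction.** SAP 6.2.1 makes no decrease part of the worst level. SAP 6.2.2 codes the outcome from 1 for worst to 5 for best, and 6.3.2.2.2 codes its binary outcome the same way. Only b − m agrees with these. The change log in SAP Table 14 shows a superseded formula with baseline minus maintenance dose. It is cited here only as evidence of intent; the contradiction is within the current text.

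**The case against.** The strongest reply is that this is a labelling slip. The lead-in in 6.2.1 joins change and reduction, Appendix A Step 4 derives the five-level response from percent change, and 6.3.2.2.1 speaks of percent and absolute change. On that reading −87.5% is simply an 87.5% reduction, and any programmer would treat it so. In 6.3.2.1.1, later minus baseline is also the right sign for the analysis of change that the section mainly serves. The patient counts depend on assumed code: the SAP gives model code but none for deriving the categories, and a catch-all clause would put the reducers in the lowest category instead of none.

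Much of this stands. The intent is clear, the sign suits the continuous change analysis, and the counts show only how conspicuous literal coding would be. The bar graph planned in 6.2.2 would expose it either way.

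What does not stand is that the text is adequate. Both sections print the change formula under the name reduction, 6.3.2.1.2 ties two endpoints to that name with positive cuts, and Appendix A Step 4 mixes the terms without giving a sign rule. The primary derivation should not depend on a programmer departing silently from the approved plan.

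**Conclusion.** The point holds. It is a sign error in the written derivation of the primary endpoint and of the first- and fourth-ranked secondaries, not an open analytic choice. As written, none of the 39 tapered doses in Table 3 counts as a reduction; corrected, all 39 do.

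The projection of 85 of 152 patients rests on the planned shares and odds ratio, on coding with no catch-all clause, and on reading the fourth planning category (printed in SAP 2.3 as starting at 0%) as starting above 0%. An error of that size would be seen, so this should be corrected before database lock but is not a likely route to a wrong primary result.

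Sample size, power, the 5 mg and 0 mg dose-level secondaries, the percent-change secondary if labelled as change, and the exacerbation rate are unaffected.

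**What to change.** In SAP 6.2.1 define absolute reduction as baseline dose minus maintenance dose, and in 6.3.2.1.1 as baseline dose minus post-baseline dose. Keep percent reduction as 100 × (absolute reduction / baseline dose). Name later minus baseline as change, and use it only for the continuous change and percent-change analyses.

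As a clarification, state in 6.3.2.2.3 that ranks are taken on the corrected reduction scale, with withdrawals and patients who lose control ranked worst.

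This takes about three lines of SAP text before database lock. It has no effect on data collection, sample size or power.

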6.2.2. Primary Analysis

The primary endpoint is the 5-level categorical percent reduction in OCS dose during weeks 20 to 24, compared to the optimized dose at baseline. The primary analysis will incorporate data from all randomized patients. Patients who are unable to maintain asthma control or who

withdraw treatment prematurely will be analyzed as part of the lowest category of response. The primary endpoint will be analyzed using a proportional odds model including factors for treatment group and the randomization strata (age and OCS dose, as defined in Section 2.4); baseline OCS dose and duration of OCS use prior to study entry will also be included as covariates. Age and OCS dose will be based on data recorded in the clinical database.

The proportional odds ratio (reslizumab/placebo) will be estimated from this model, representing the ratio of the odds of a patient outcome being in a higher OCS dose reduction category for reslizumab compared to placebo. The estimated odds ratio, 95% CI, and p-value will be reported. A frequency distribution bar graph will be provided for the number of patients in each of the 5 categories by treatment group.

The following sample Statistical Analysis Software (SAS[®]) code pertains to the primary efficacy analysis of categorical dose reduction; ‘treatment’ is the randomized group (‘0’=placebo) and ‘out_cat5’ is the 5-level response category (1=worst category, ..., 5=best category):

```
proc genmod data=<<>> order=internal descending;
  class treatment (param=ref ref='0') strata1 strata2;
  model out_cat5 = treatment strata1 strata2 ocsbase ocsdur
    / dist=mult link=cumlogit aggregate=treatment type3;
  estimate "odds ratio" treatment 1 -1 / exp;
  ods output parameterestimates=<<>>;
run;
```

Note that multicollinearity occurs when there is a high degree of correlation among two or more of the independent variables included within a linear model; it can lead to unstable and unreliable estimates of the regression coefficients. It is recognized that, in the model described above for the primary endpoint (and for the models described subsequently in Section 6.3.2.2 for the related secondary endpoints), the categorical variable for OCS dose randomization strata is expected to be correlated to the continuous variable for OCS dose at baseline. The presence of collinearity between these variables will tend to make the estimates for each of these coefficients unstable, as well as increase the standard errors of their estimated coefficients. However, since the variable of interest in these models is the effect of treatment, and OCS dose at baseline has been included in the model as a control variable, estimation of the regression coefficient for treatment should be unaffected by the presence of this collinearity and the performance of OCS dose as a control variable in the model should not be impaired.

6.2.3. Sensitivity Analyses for the Primary Variable

The following list of sensitivity analyses are pre-specified for this study, with an aim toward assessing the robustness of the primary efficacy results:

- The primary analysis with control variables (age and OCS dose) based on data recorded in the IRT (as randomized). This analysis will only be performed if the number of discrepancies between data recorded in the IRT and the clinical database are sufficiently large (eg, 5% of total population).
- Per-protocol: analysis of the primary endpoint, based on the PP analysis set.
- Additional analysis including data collected after early withdrawal from treatment.

- If a patient elects to withdraw from treatment (or is discontinued from treatment by the investigator), every attempt will be made to continue the assessments subsequent to his/her withdrawal from the study. If the patients agrees to remain in the study, they will continue to receive study prednisone treatment for the remainder of their participation in the study.
- In this analysis, patients will be categorized according to the percent dose reduction at 24 weeks regardless of whether they withdrew early from treatment or completed treatment. For patients who withdraw early and for whom the sponsor fails to retrieve data after withdrawal despite all attempts to contact the patients, multiple imputation will be performed to determine the categorization according to the percent dose reduction at 24 weeks. The multiple imputations will use the post withdrawal data observed for patients who withdrew early and for which the sponsor succeeded to retrieve the data. The methodology and algorithm used for imputations will be detailed in [Appendix A](#).
- “Tipping point” multiple imputation: analysis of the primary endpoint to assess deviations from missing at random (MAR). The details regarding this analysis are provided in [Appendix B](#).

6.2.4. Subgroup Analyses for the Primary Variable

The primary efficacy variable will additionally be examined for the subgroups defined in Section 3.4. The analysis will be similar to the analysis described for the primary endpoint (Section 6.2.2). An interaction p-value will be derived from a separate proportional odds model including additional terms for subgroup and treatment by subgroup interaction. Subgroup analyses for the primary efficacy variable will be presented graphically using forest plots.

6.3. Secondary Efficacy Variable(s) and Analysis

As described previously in Section 4.5, an on-treatment approach will be adopted as the primary analysis for the efficacy variables assessed by-visit. In this analysis, the treatment period will be defined from the first dose of study drug to the end of treatment (week 24) visit for patients who completed treatment and from the first dose of study drug to the last dose of study drug (+4 weeks) for patient who discontinued treatment early. Measurements collected outside of these defined timeframes will be excluded from the analyses and endpoint will be defined within these timeframes. All results will be included in the patient listings. For selected key variables, additional sensitivity analyses may also be performed in which all post-baseline measurements collected during the study will be included and endpoint will be defined within this extended timeframe.

6.3.1. Secondary Variables

The secondary efficacy endpoints for this study are as follows:

- Proportion of patients achieving $\geq 50\%$ reduction in OCS dose at weeks 20 to 24 relative to the OCS dose at the date of randomization (DoR)/baseline, while maintaining asthma control

- Proportion of patients achieving dose reduction to ≤ 5 mg daily dose at weeks 20 to 24, while maintaining asthma control
- Percent change from DoR/baseline in OCS dose at weeks 20 to 24
- Proportion of patients achieving less than 5 mg decrement in OCS dose (ie, the minimal and non-responders) at weeks 20 to 24 compared with the OCS dose at DoR/baseline, while maintaining asthma control
- Annualized rate of clinical asthma exacerbations requiring a burst of systemic corticosteroid (injection, or if oral, at least a doubling from the current OCS dose for at least 3 days); an asthma-specific hospital admission; or an asthma-specific emergency department visit during the treatment period (weeks 0 to 24)
- Proportion of patients discontinuing OCS at weeks 20 to 24, while maintaining asthma control

Testing of the secondary variables will be performed using the sequential testing procedure in the order specified above, as described in Section 4.3.

6.3.2. OCS Dose

Note: All analyses related to OCS dose will be discussed within this section; this will include the planned analyses related to the list of secondary variables (in Section 6.3.1), as well as additional planned analyses related to OCS dose that have not otherwise been specified. The analysis of OCS dose as a continuous variable will be discussed separately from the analysis of OCS dose as a categorical variable.

6.3.2.1. Variable Definition

6.3.2.1.1. Continuous Variable

The post-baseline values for OCS dose and corresponding values for absolute and percent change from baseline will be calculated as follows:

- **Baseline dose** = the prescribed optimized OCS dose following the OCS optimization period (Table 8)
- **Post-baseline dose** = mean of all daily OCS doses during each defined analysis period (Table 8)
- **Absolute reduction** = post-baseline dose – baseline dose
- **Percent reduction** = $100 \times (\text{absolute reduction} / \text{baseline dose})$

Table 8: Definition of Analysis Days for OCS Dose

Analysis period	Start day	Stop day
Baseline Dose	Day of first dose of study drug	N/A
Baseline to Week 4	Day of first dose of study drug + 1 day	Day of W4 Visit
Week 4 to Week 8	Day of W4 Visit + 1 day	Day of W8 Visit
Week 8 to Week 12	Day of W8 Visit + 1 day	Day of W12 Visit
Week 12 to Week 16	Day of W12 Visit + 1 day	Day of W16 Visit
Week 16 to Week 20	Day of W16 Visit + 1 day	Day of W20 Visit
Week 20 to Week 24 (Maintenance Dose)	Day of W20 Visit + 1 day	Day of W24 Visit

DoR=Day of Randomization

6.3.2.1.2. Categorical Variable

The proportion of patients achieving a 50% or greater reduction in OCS dose at weeks 20 to 24 will be based on the percent reduction from baseline to weeks 20 to 24. The categories for this analysis are:

- 50-100% reduction
- <50% reduction, or loss of baseline asthma control during weeks 20 through 24, or discontinuation from study drug

The proportion of patients who achieve a reduction of their OCS dose to less than or equal to 5 mg at weeks 20 to 24 will be based on the observed post-baseline value during weeks 20 to 24. The categories for this analysis are:

- ≤ 5 mg
- > 5 mg, or loss of baseline asthma control during weeks 20 through 24, or discontinuation from study drug

The proportion of patients who achieve a total reduction (discontinuation) of their OCS dose at weeks 20 to 24 will be based on the observed post-baseline value during weeks 20 to 24. The categories for this analysis are:

- =0 mg
- > 0 mg, or loss of baseline asthma control during weeks 20 through 24, or discontinuation from study drug

Note: Total reduction implies no OCS use during the entire period (weeks 20 to 24).

The proportion of patients achieving less than a 5 mg reduction in OCS dose at weeks 20 to 24 will be based on the absolute reduction from baseline to weeks 20 to 24. The categories for this analysis are:

- ≥ 5 mg reduction

- <5 mg reduction, or loss of baseline asthma control during weeks 20 through 24, or discontinuation from study drug

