4.4. Randomization criteria

After completion of the optimization/run-in period, patients may continue in the study if they meet all of the following criteria:

- a. The patient must be using an average daily dose of no less than 5 mg of prednisone after OCS optimization. A patient requiring less than 5 mg of prednisone to maintain control should not be randomized.
- b. The patient must be using an average daily dose of no more than 40 mg of prednisone after OCS optimization. A patient requiring more than 40 mg of prednisone to maintain control should not be randomized.
- c. The patient should not have had an asthma exacerbation during the run-in period, defined as requiring a burst of systemic corticosteroid for an asthma worsening (injection, or if oral, at least a doubling from the current OCS dose for at least 3 days); an asthma-specific hospital admission; or an asthma-specific emergency department visit.

- d. The patient must have completed at least 4 days of diary entries (or any combination of 4 morning and 4 evening recordings) during the last 7 days of the run-in period.

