2.1.4. Treatment Period

Patients continuing to meet eligibility criteria on the day of randomization (day 1, week 0) will be randomly assigned in a 1:1 ratio to receive placebo or reslizumab 110 mg once every 4 weeks

through week 20, followed by an EOT visit at week 24. Patients will begin treatment on day 1 after completing baseline assessments, and they will return to the research facility for outpatient visits every 4 weeks through week 24 (EOT visit) for safety, PK, PD, immunogenicity, and efficacy assessments as applicable.

During the treatment period, the patient will continue his/her usual non-OCS background asthma medication without change; the OCS dose will be tapered per protocol. The treatment period consists of the following:

- **Induction:** The minimally effective dose of OCS will be maintained, unchanged, during the first 4 weeks of the treatment period to allow sufficient time for any potential treatment effect to become established.
- **OCS reduction:** The minimally effective OCS dose will be reduced per protocol at scheduled clinic visits from the beginning of week 5 (ie, end of the induction period) through week 20, as long as all 5 criteria in [Table 2](#) are met and there are no clinical manifestations of adrenal insufficiency. These 5 eligibility criteria assure that the patient's asthma control is not significantly worsened compared to baseline. The last possible dose reduction can occur at week 20. The algorithm for OCS reductions during the treatment period is given in [Table 3](#). If the OCS dose could not be decreased, it should be held constant or may be increased to a previous level, at the investigator's discretion, until dose reduction criteria are met.
- **Maintenance:** OCS dose will be held stable from week 20 through EOT at week 24.

Table 2: Eligibility Criteria for Scheduled Oral Corticosteroid Reductions During the Treatment Period (Must Meet All)

1.	Forced expiratory volume in 1 second (FEV ₁) ≥80% of baseline ^a
2.	AM PEF ≥80% of baseline mean AM PEF on at least 5 of the 7 days preceding the visit
3.	Mean nighttime awakenings due to asthma requiring rescue inhaler over the preceding 7 days ≤150% increase over the baseline period
4.	Reliever bronchodilator inhaler use does not exceed 150% of the baseline inhaler use per 24 hours on more than 2 of the preceding 7 days
5.	No increase in OCS dose since the previous visit ^b

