^a Baseline for clinic visit measures (FEV₁) is the DoR value. Baseline for diary measures is the average over the 7 days prior to DoR.

^b If a dose increase results in a return to the previous dose, then it is acceptable to attempt dose decrease again at the investigator's discretion.

AM=morning; DoR=date of randomization; FEV₁=forced expiratory volume in 1 second; PEF=peak expiratory flow; OCS=oral corticosteroid.

Table 3: Oral Corticosteroid Decrements During the Treatment Period

Time Course	Oral OCS Dose (mg/day)								
Optimized OCS dose	40	35	30	25	20	15	10	7.5	5
1 st reduction	30	25	20	15	10	10	7.5	5	2.5
+ 4 weeks	20	15	10	10	7.5	7.5	5	2.5	0
+ 4 weeks	10	10	5	5	5	5	2.5	0	
+ 4 weeks	5	5	2.5	2.5	2.5	2.5	0		
+ 4 weeks	2.5	2.5	0	0	0	0			

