2.1.4.1. Handling of Asthma Exacerbations During the Treatment Period

Patients should be treated with an OCS burst: 40 to 60 mg (or at least double the current dose) of OCS tapered over a 7- to 10-day period to a new maintenance dose of 2.5 mg above the pre-burst dose. It is understood that im or iv corticosteroid may also be administered as part of the treatment of the asthma exacerbation. If a second OCS burst (doubling of current dose) is required, the patient should be maintained on a fixed OCS dose without any tapering attempts for the remainder of the double-blind treatment phase and the follow-up period.

Patients who complete all scheduled visits will have final procedures and assessments performed at the EOT visit (visit 19). Patients who withdraw from the study before completing the 24-week treatment period will have visit 19 (week 24 ± 7 days or early termination) procedures and assessments performed at their final visit. Patients will return for a follow-up evaluation 8 weeks (±7 days) after the EOT visit in this study for assessment of pre-bronchodilator spirometry, ACQ-6 score, PK samples, adverse events, blood eosinophils, CAEs and related health care utilizations, and blood for ADA.

The assessments and procedures performed during each study visit are detailed in [Table 4](#). If a patient elects to withdraw (or is discontinued from treatment by the investigator), every attempt will be made to continue the assessments subsequent to his/her withdrawal from the study.

Table 4: Study Procedures and Assessments

Procedures and assessments	Pretreatment		V12 Start run-in	Double-blind treatment period (visit/week)							Follow-up	Late follow-up
	V1	V2-V11		V13 ^a	V14 ^a	V15 ^a	V16 ^a	V17 ^a	V18 ^a	V19 ^a	V20	V21
	Start of screening period	Standardize and optimize maintenance OCS ^{abc}										
	Week -14 ^d	Between weeks -12 and -3		W -2	DoR	W4±7d	W8±7d	W12±7d	W16±7d	W20±7d	W24±7d/ EOT/ early termination	W32/EOT + 8w ±7d
Informed assent/consent	X											
Medical history	X											
Medication history	X											
Inclusion and/or exclusion criteria	X	X ^e	X	X								
Randomization criteria				X								
Reversibility testing ^f	X											
Pregnancy testing ^g	X			X	X	X	X	X	X	X	X	
Blood for HIV, hepatitis B, and hepatitis C	X											
CBC with differential ^h	X	X	X	X	X	X	X	X	X	X	X	
Serum chemistry tests ⁱ	X			X	X ^j	X ^j	X	X ^j	X ^j	X		
Urinalysis	X											
Full physical examination ^k	X											

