2.3. Sample Size and Power Considerations

The primary efficacy variable and endpoint for this study is the percent reduction in the daily OCS dose during weeks 20 to 24 as compared with the dose at the end of the optimization phase. The study will be considered positive if the measure meets statistical significance at the respective predefined significance level. A statistically significant effect of reslizumab over placebo, as measured by the primary efficacy variable, is required to establish the efficacy of reslizumab treatment.

The sample size was calculated based on the following assumptions:

- Categorical reduction in OCS dose after 24 weeks of treatment will have the following distribution for the placebo group (based on [Bel et al 2014](#)):
 - 10.9% percent of subjects will have 90% to 100% reduction
 - 7.9% percent of subjects will have 75% to <90% reduction
 - 14.8% percent of subjects will have 50% to <75% reduction
 - 10.8% percent of subjects will have 0% to <50% reduction
 - 55.6% percent of subjects will have no reduction, loss of asthma control, or discontinuation from study drug
- The overall odds ratio between reslizumab and placebo based on proportional odds model will be 2.63
- Alpha level of 0.05

Based on the above assumptions, a sample size of 76 subjects per group will provide 90% power to detect a significant effect of reslizumab over placebo on the probability for a higher categorical reduction of OCS dose.

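### The secondary on reducing OCS to 5 mg or less ignores baseline dose, so a controlled, on-drug 5 mg entrant with no decrease counts as a responder

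*SAP*

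**What the plan says.** Protocol 9.5.2 and SAP 6.3.1 list the second secondary as the proportion of patients with a dose reduction to 5 mg or less at weeks 20 to 24 with asthma control maintained. It belongs to the type I error hierarchy: "Testing of the secondary variables will be performed using the sequential testing procedure in the order specified above".

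SAP 6.3.2.1.2 gives the scoring. The defining sentence is framed around patients whose dose comes down, and then fixes the basis of the count: "OCS dose to less than or equal to 5 mg at weeks 20 to 24 will be based on the observed post-baseline value". Two exhaustive categories follow. One is a weeks 20 to 24 dose of 5 mg or less. The other is a dose above 5 mg, or loss of control, or stopping study drug. Neither mentions the baseline dose or a decrease.

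Other passages that bear on it:

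- Entry floor (Protocol 4.4): "The patient must be using an average daily dose of no less than 5 mg of prednisone after OCS optimization". SAP Table 3, "Oral Corticosteroid Decrements During the Treatment Period", has a 5 mg starting column.
- Failed taper (SAP 2.1.4): "If the OCS dose could not be decreased, it should be held constant or may be increased to a previous level".
- Lowest category of the primary endpoint (SAP 6.2.1): "No decrease in OCS, or loss of baseline asthma control during weeks 20 through 24, or discontinuation from study drug".
- Model (SAP 6.3.2.2.2): logistic regression with the primary analysis covariates, which include baseline OCS dose and the OCS stratum.

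**The concern.** The name and the categories disagree for one group, patients who enter on exactly 5 mg. Anyone entering above 5 mg must come down to qualify. A 5 mg entrant need not, because 5 mg already satisfies the dose criterion. If that patient's dose never falls, control is kept and study drug is continued, the SAP records a dose-reduction success.

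The reported proportion, its odds ratio and the bar graph would then include patients with no reduction, in a test that can support an inferential claim. Adjusting for baseline dose changes the comparison between arms; it does not change who is counted as a responder.

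**Working it through.** **1. Classification.** Take a patient with baseline 5 mg, mean weeks 20 to 24 dose 5 mg, control kept, on drug.

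| Endpoint (SAP) | Basis | Result |
|---|---|---|
| Primary (6.2.1) | percent reduction, 0% | lowest category |
| At least 50% reduction (6.3.2.1.2) | percent reduction, 0% | non-responder |
| 5 mg or less (6.3.2.1.2) | observed dose, 5 ≤ 5 | **responder** |
| OCS stopped (6.3.2.1.2) | observed dose, 5 > 0 | non-responder |

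**2. Can this patient occur?** Yes. A taper step requires all five Table 2 criteria, including morning PEF, awakenings and reliever use, and no clinical signs of adrenal insufficiency. Loss of control is a different test: week 24 FEV₁, week 24 ACQ-6, and an exacerbation in weeks 20 to 24. A 5 mg entrant can fail a diary criterion, stay on 5 mg, and still count as controlled.

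**3. The plan's own figure.** No power is stated for this secondary. For the primary, SAP 2.3 gives placebo category rates of 10.9, 7.9, 14.8, 10.8 and 55.6%, and "The overall odds ratio between reslizumab and placebo based on proportional odds model will be 2.63". The Whitehead formula, two-sided 0.05 and 90% power, gives

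n per arm = 6(1.960 + 1.282)² / [(ln 2.63)² × (1 − 0.0976)] = 74.7,

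which rounds up to 75 against the stated 76. The design figure reproduces.

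**4. Inputs for the illustration.**

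- At least 50% reduction, placebo: 10.9 + 7.9 + 14.8 = 33.6%. Active: odds 0.336/0.664 × 2.63 = 1.331, or 57.1%.
- Any decrease (d), placebo: 33.6 + 10.8 = 44.4%. Active: odds 0.444/0.556 × 2.63 = 2.100, or 67.7%.
- f = share entering on 5 mg. Not in the documents.
- q = share of 5 mg entrants in the lowest category who are unchanged, controlled and on drug. Not in the documents. It is below 1, because that category also holds loss of control and discontinuation. An exacerbation lowers it further, since the patient goes "to a new maintenance dose of 2.5 mg above the pre-burst dose".
- The rate of at least 50% reduction stands in for reaching 5 mg among all other entrants. This is exact only from a 10 mg start: the cut needed is 33% from 7.5 mg and 87.5% from 40 mg.

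**5. Formulas.** The response rate in 5 mg entrants is d + q(1 − d) as written, and d if a decrease is required. The overall rate is (1 − f) × (rate of at least 50% reduction) + f × (5 mg entrant rate). Power is the unadjusted two-proportion formula with pooled variance, 76 per arm, two-sided 0.05. At f = 0:

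[(0.571 − 0.336)√76 − 1.96√(2 × 0.4535 × 0.5465)] / √(0.2231 + 0.2450) = 0.669/0.684 = 0.977, so power is 83.6%.

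**6. Results.**

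| Scoring | q placebo / active | f = 5% | f = 10% | f = 20% |
|---|---|---|---|---|
| Decrease required | n/a | 83.5% | 83.4% (OR 2.62) | 83.2% (OR 2.61) |
| As written | 0.25 / 0.25 | 82.5% | 81.3% (OR 2.55) | 79.1% (OR 2.48) |
| As written | 0.50 / 0.50 | 81.4% | 79.2% (OR 2.48) | 74.6% (OR 2.36) |
| As written | 0.25 / 0.50 | not tabulated | 84.0% (OR 2.63) | 84.6% (OR 2.65) |
| As written | 0.50 / 0.75 | not tabulated | 82.0% | 80.8% |

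Extra responders per arm are 76 × f × q × (1 − d). At f = 10% and q = 0.25 in both arms: 76 × 0.10 × 0.25 × 0.556 = 1.1 on placebo and 76 × 0.10 × 0.25 × 0.323 = 0.6 on active. At f = 20% and q = 0.5 they are 4.2 and 2.5.

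With equal q of 0.25 to 0.5, unchanged patients make up 4% to 7% of placebo and 1% to 3% of active responders at f = 10%. At f = 20% the shares are 7% to 14% and 3% to 5%.

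**7. Break-even.** The arms gain equal numbers when q(active)/q(placebo) = 0.556/0.323 = 1.72. Below that ratio the extra responders fall mostly on placebo; above it, mostly on active.

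**The case against.** The strongest reply is that this is a matter of labelling. The defining sentence does speak of a reduction, and only the categories omit it. An absolute low-dose target is a coherent endpoint, and the hierarchy already has baseline-relative measures on either side of it. Few patients may be involved: an affected patient must enter on exactly 5 mg, get no lasting decrease from five scheduled attempts, and still pass the control test. At q = 0.10 in both arms and f = 10%, the effect is about 0.4 extra placebo and 0.25 extra active responders, with power 82.6% against 83.4%. The illustration is also unadjusted and uses a rough proxy.

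The points on size stand. The size is unknown and could be trivial, and the power figures cannot carry the argument. The labelling point stands in part: an absolute target would be legitimate, but it would then need a different name. Programming follows the categories, and under them a patient with no reduction is counted as reduced. Nor do the other endpoints isolate these patients. The primary pools no decrease with loss of control and discontinuation, and in the secondary on a decrement below 5 mg, a 5 mg entrant who halves to 2.5 mg sits in the same category as one who is unchanged.

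**Conclusion.** The concern holds. That the categories count an unreduced patient as a responder follows from the definitions and rests on no assumption. It is confined to patients randomised on exactly 5 mg.

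Its effect on the estimate cannot be determined from the documents, in size or in direction, because f and q are not given. In the cases worked above, marginal power for this test runs from 74.6% to 84.6%, against about 83% with a decrease required. These are unadjusted figures under assumed f and q and the 50% proxy. They are not the probability that this test stops the sequence. Type I error and the primary result are not affected. This should be corrected, but it does not threaten the trial's main conclusion.

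**What to change.** Before unblinding, choose one of two changes to SAP 6.3.2.1.2.

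1. If a reduction is meant, define the responder as a mean weeks 20 to 24 dose of 5 mg or less **and** below the baseline dose, with control maintained and study drug not discontinued, in all randomised patients. For 5 mg entrants this means any decrease.
2. If an absolute target is meant, keep the scoring and rename the endpoint as a dose of 5 mg or less at weeks 20 to 24. Then report 5 mg entrants separately by arm as decreased; unchanged but controlled and on drug; or lost control or stopped drug.

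Either costs one line of SAP wording, plus one descriptive table under the second. The first alters a prespecified endpoint in the hierarchy, so it should be recorded as an amendment. No new data are needed, no randomised patient leaves the analysis, and no dosing rule changes.
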